7.2 Dose modification and toxicity management guidelines for pembrolizumab

Dose modification and toxicity management for immune-related AEs associated with Pembrolizumab

AEs associated with pembrolizumab exposure may represent an immunologic etiology. These immune-related AEs (irAEs) may occur shortly after the first dose or several months after the last dose of pembrolizumab treatment and may affect more than one body system simultaneously. Therefore, early recognition and initiation of treatment is critical to reduce complications. Based on existing clinical trial data, most irAEs were reversible and could be managed with interruptions of pembrolizumab, administration of corticosteroids and/or other supportive care. For suspected irAEs, ensure adequate evaluation to confirm etiology or exclude other causes. Additional procedures or tests such as bronchoscopy, endoscopy, skin biopsy may be included as part of the evaluation. Based on the severity of irAEs, withhold or permanently discontinue pembrolizumab and administer corticosteroids. Dose modification and toxicity management guidelines for irAEs associated with pembrolizumab are provided in Table 7.9.

Table 7.9: Dose modification and toxicity management guidelines for immune-related AEs associated with Pembrolizumab.

General instructions:				
Immune-related AEs	Toxicity grade or conditions (CTCAE v.5.0)	Action taken to pembrolizumab	irAE management with corticosteroid and/or other therapies	Monitor and follow-up
Pneumonitis	Grade 2	Withhold	
Administer corticosteroids (initial dose of 1-2mg/kg prednisone or equivalent) followed by taper	
Monitor subjects for signs and symptoms of pneumonitisEvaluate subjects with suspected pneumonitis with radiographic imaging and initiate corticosteroid treatmentAdd prophylactic antibiotics for opportunistic infections
	Grade 3 or 4, or recurrent grade 2	Permanently discontinue		

Diarrhea / colitis	Grade 2 or 3	Withhold	
 Administer corticosteroids (initial dose of 1-2mg/kg prednisone or equivalent) followed by taper 	
 Monitor subjects for signs and symptoms of enterocolitis (i.e., diarrhea, abdominal pain, blood or mucus in stool with or without fever) and of bowel perforation (i.e., peritoneal signs and ileus). Subjects with \geq Grade 2 diarrhea suspecting colitis should consider GI consultation and performing endoscopy to rule out colitis. Subjects with diarrhea/colitis should be advised to drink liberal quantities of clear fluids. If sufficient oral fluid intake is not feasible, fluid and electrolytes should be substituted via IV infusion.
	Grade 4	Permanently discontinue		
AST / ALT elevation or Increased Bilirubin	Grade 2	Withhold	
 Administer corticosteroids (initial dose of 0.5-1mg/kg prednisone or equivalent) followed by taper 	
 Monitor with liver function tests (consider weekly or more frequently until liver enzyme value returned to baseline or is stable)
	Grade 3 or 4	Permanently discontinue	
 Administer corticosteroids (initial dose of 1-2mg/kg prednisone or equivalent) followed by taper 	
Type 1 diabetes mellitus (T1DM) or Hyperglycemia	Newly onset T1DM or Grade 3 or 4 hyperglycemia associated with evidence of β -cell failure	Withhold	
 Initiate insulin replacement therapy for subjects with T1DM Administer anti-hyperglycemic in subjects with hyperglycemia 	
 Monitor subjects for hyperglycemia or other signs and symptoms of diabetes.
Hypophysitis	Grade 2	Withhold	
 Administer corticosteroids and initiate hormonal replacements as clinically indicated. 	
 Monitor for signs and symptoms of hypophysitis (including hypopituitarism and adrenal insufficiency)
	Grade 3 or 4	Withhold or permanently discontinue ¹		
Hyperthyroidism	Grade 2	Continue	
 Treat with non-selective beta-blockers (e.g. propranolol) or thionamides as appropriate 	
 Monitor for signs and symptoms of thyroid disorders.
	Grade 3 or 4	Withhold or Permanently discontinue ¹		

Hypothyroidism	Grade 2-4	Continue	
 Initiate thyroid replacement hormones (e.g. levothyroxine or liothyroinine) per standard of care 	
 Monitor for signs and symptoms of thyroid disorders.
Serum Creatinine Increased	Grade 2	Withhold	
 Administer corticosteroids (prednisone 1-2mg/kg or equivalent) followed by taper. 	
 Monitor changes of renal function
	Grade 3 or 4	Permanently discontinue		
All Other immune-related AEs	Grade 3, or intolerable/ persistent Grade 2	Withhold	
 Based on severity of AE administer corticosteroids 	
 Ensure adequate evaluation to confirm etiology or exclude other causes
	Grade 4 or recurrent Grade 3	Permanently discontinue		

NOTES:

- Withhold or permanently discontinue pembrolizumab is at the discretion of the investigator or treating physician.
- For subjects with Grade 3 or 4 immune-related endocrinopathy where withhold of pembrolizumab is required, pembrolizumab may be resumed when AE resolves to \leq Grade 2 and is controlled with hormonal replacement therapy or achieved metabolic control (in case of T1DM)

Pembrolizumab may cause severe or life threatening infusion-reactions including severe hypersensitivity or anaphylaxis. Signs and symptoms usually develop during or shortly after drug infusion and generally resolve completely within 24 hours of completion of infusion. Dose modification and toxicity management guidelines on pembrolizumab associated infusion reaction are provided in Table 7.10.

Table 7.10: Pembrolizumab Infusion Reaction Dose modification and Treatment Guidelines

NCI CTCAE Grade	Treatment	Premedication at Subsequent Dosing
Grade 1 Mild reaction; infusion interruption not indicated; intervention not indicated	Increase monitoring of vital signs as medically indicated until the subject is deemed medically stable in the opinion of the investigator.	None


Grade 2
 
Requires therapy or infusion interruption but responds promptly to symptomatic treatment (e.g., antihistamines, NSAIDs, narcotics, IV fluids); prophylactic medications indicated for ≤24 hrs
	
Stop Infusion.
 
Additional appropriate medical therapy may include but is not limited to:
 
IV fluids Antihistamines NSAIDs Acetaminophen Narcotics
 
Increase monitoring of vital signs as medically indicated until the subject is deemed medically stable in the opinion of the investigator. If symptoms resolve within 1 hour of stopping drug infusion, the infusion may be restarted at 50% of the original infusion rate (e.g., from 100 mL/hr to 50 mL/hr). Otherwise dosing will be held until symptoms resolve and the subject should be premedicated for the next scheduled dose.
 
Subjects who develop Grade 2 toxicity despite adequate premedication should be permanently discontinued from further study drug treatment
	
Subject may be premedicated 1.5h (± 30 minutes) prior to infusion of pembrolizumab with:
 
Diphenhydramine 50 mg po (or equivalent dose of antihistamine). Acetaminophen 500-1000 mg po (or equivalent dose of analgesic).

Grades 3 or 4
 
Grade 3: Prolonged (i.e., not rapidly responsive to symptomatic medication and/or brief interruption of infusion); recurrence of symptoms following initial improvement; hospitalization indicated for other clinical sequelae (e.g., renal impairment, pulmonary infiltrates)
 
Grade 4: Life-threatening; pressor or ventilatory support indicated
	
Stop Infusion.
 
Additional appropriate medical therapy may include but is not limited to:
 
Epinephrine** IV fluids Antihistamines NSAIDs Acetaminophen Narcotics Oxygen Pressors Corticosteroids
 
Increase monitoring of vital signs as medically indicated until the subject is deemed medically stable in the opinion of the investigator. Hospitalization may be indicated.
 
**In cases of anaphylaxis, epinephrine should be used immediately.
 
Subject is permanently discontinued from further study drug treatment.
	
No subsequent dosing

Appropriate resuscitation equipment should be available at the bedside and a physician readily available during the period of drug administration.

For further information, please refer to the Common Terminology Criteria for Adverse Events v.5.0 (CTCAE) at <http://ctep.cancer.gov>

Other allowed dose interruption for pembrolizumab

Pembrolizumab may be interrupted for situations other than treatment-related AEs such as medical / surgical events or logistical reasons not related to study therapy. Subjects should be placed back on study therapy within 3 weeks of the scheduled interruption, unless otherwise discussed with the study sponsor (principal investigator). The reason for interruption should be documented in the patient's study record. Patients with a planned interruption may continue on the study with monotherapy of the other agent. Patients may also continue on the study with a planned permanent discontinuation of one of the study medications.

7.3 Contraception

Pembrolizumab may have adverse effects on a fetus in utero. Furthermore, it is not known if pembrolizumab has transient adverse effects on the composition of sperm.

For this trial, male subjects will be considered to be of non-reproductive potential if they have azoospermia (whether due to having had a vasectomy or due to an underlying medical condition).

Female subjects will be considered of non-reproductive potential if they are either:

(1) postmenopausal (defined as at least 12 months with no menses without an alternative medical cause; in women < 45 years of age a high follicle stimulating hormone (FSH) level in the postmenopausal range may be used to confirm a post-menopausal state in women not using hormonal contraception or hormonal replacement therapy. In the absence of 12 months of amenorrhea, a single FSH measurement is insufficient.);

OR

(2) have had a hysterectomy and/or bilateral oophorectomy, bilateral salpingectomy or bilateral tubal ligation/occlusion, at least 6 weeks prior to screening;

OR

(3) has a congenital or acquired condition that prevents childbearing.

Female and male subjects of reproductive potential must agree to avoid becoming pregnant or impregnating a partner, respectively, while receiving study drug and for 120 days after the last dose of study drug by complying with one of the following:

(1) practice abstinence[†] from heterosexual activity;

OR

(2) use (or have their partner use) acceptable contraception during heterosexual activity.

Acceptable methods of contraception are[‡]:

Single method (one of the following is acceptable):

- Intrauterine device (IUD)

- Vasectomy of a female subject's male partner
- Contraceptive rod implanted into the skin

Combination method (requires use of two of the following):

- Diaphragm with spermicide (cannot be used in conjunction with cervical cap/spermicide)
- Cervical cap with spermicide (nulliparous women only)
- Contraceptive sponge (nulliparous women only)
- Male condom or female condom (cannot be used together)
- Hormonal contraceptive: oral contraceptive pill (estrogen/progestin pill or progestin-only pill), contraceptive skin patch, vaginal contraceptive ring, or subcutaneous contraceptive injection

†Abstinence (relative to heterosexual activity) can be used as the sole method of contraception if it is consistently employed as the subject's preferred and usual lifestyle and if considered acceptable by local regulatory agencies and ERCs/IRBs. Periodic abstinence (e.g., calendar, ovulation, sympto-thermal, post-ovulation methods, etc.) and withdrawal are not acceptable methods of contraception.

‡If a contraceptive method listed above is restricted by local regulations/guidelines, then it does not qualify as an acceptable method of contraception for subjects participating at sites in this country/region.

Subjects should be informed that taking the study medication may involve unknown risks to the fetus (unborn baby) if pregnancy were to occur during the study. In order to participate in the study subjects of childbearing potential must adhere to the contraception requirement (described above) from the day of study medication initiation (or 14 days prior to the initiation of study medication for oral contraception) throughout the study period up to 120 days after the last dose of trial therapy. If there is any question that a subject of childbearing potential will not reliably comply with the requirements for contraception, that subject should not be entered into the study.

7.4 Supportive Care

All supportive measures consistent with optimal patient care will be given throughout the study.

8 STUDY CALENDAR

1 cycle = 3 weeks ± 3 days

Examination	Pre-screening ²³	Screening ¹	C1, 5, 9... Day 1 ²	C2, 6, 10... Day 1	C3, 7, 11... Day 1	C4, 8, 12... Day 1	End of Treatment ²⁰	Follow-up ²¹
Informed consent	X	X						
Medical history		X						
Eligibility criteria	X	X						
Vital signs, weight		X	X	X	X	X	X	
Height		X						
Physical examination ³	X	X	X	X	X	X	X	
ECOG performance status		X	X	X	X	X	X	
Viral Hepatitis Screening ⁴	X							
Smoking History		X						
Hematology ⁵	X	X	X	X	X	X	X	
Chemistry ⁶	X	X	X	X	X	X	X	
LDH, Lipase, Lipid Panel, GGT ⁷	X					X	X	
BNP ²²		X				X	X	
Urinalysis ⁸	X	X	X	X	X	X	X	
Coagulation ⁹	X					X	X	
Thyroid Function Test ¹⁰	X					X	X	
Pregnancy test ¹¹	X		X			X		
ECG ¹²		X				X		
Concomitant Medications					X			
Adverse Event Assessment					X			
CT Scans (c, a, p) ¹³	X					X ¹³	X	X ²¹
Bone Scans ¹⁴	X	X					X	X
Optional Tissue for Correlative Studies ¹⁵	X	(X) ¹⁵				X		
Optional Blood for Correlative Studies ¹⁶			X	X	X	X	X	
Optional Stool for Correlative Studies ¹⁷			X	X	X	X	X	
Optional Stool Questionnaire to accompany Optional Stool sample collection for Correlative Studies ¹⁷			X	X	X	X	X	
Cabozantinib ¹⁸			X	X	X	X		
Pembrolizumab ¹⁹			X	X	X	X		
Survival Follow Up								X ²¹

1. Screening procedures must be completed within 28 days prior to C1D1 ALL Pre-study/Screening procedures should be completed within 4 weeks of study enrollment - with the exception of laboratory tests which need to be completed within 14 days prior to study treatment.
2. Labs on C1D1 do not need to be repeated if conducted within 14 days of start of treatment
3. Physical Exam including oral examination
4. Hepatitis screening will be performed at screening if clinically indicated.
5. Hematology includes CBC with differential and platelets (must be completed within 2 weeks prior to study enrollment).
6. Chemistry includes Albumin, Alkaline Phosphatase, Aspartate Aminotransferase, Alanine Aminotransferase, Total Bilirubin, Calcium, Carbon Dioxide, Creatinine, Chloride, Glucose, Potassium, Protein, Sodium, Urea Nitrogen, phosphorus and magnesium (must be completed within 14 days prior to study enrollment at screening)
7. Additional Labs: Lactate Dehydrogenase, Lipase, Lipid Panel, Gamma Glutamyl Transferase, and should be collected at baseline and at every 4th cycle.
8. Urinalysis including urine protein/creatinine ratio on day 1 of each cycle. Both spot protein/creatinine and the 24 protein/creatinine evaluations are acceptable.
9. Coagulation labs to be collected: PT/INR, APTT. Coagulation panel will only be required at EOT if patients are on active anticoagulant therapy and require monitoring.
10. Free T4, Free T3 and TSH must be performed at baseline and at least every 4th cycle during treatment
11. Pregnancy test (serum or urine- if urine is positive it must be confirmed with serum test) must be done at screening for all women of childbearing potential and every even cycle (2,4,6 ...etc.) during treatment (must be completed within 72hr prior to study enrollment)
12. ECG should be collected at screening (see section 9 for QTcF eligibility details at screening) and at every 4th cycle.
13. CT scans of chest, abdomen and pelvis will be repeated every 4th cycle during treatment within 1 week prior to the corresponding cycle (e.g., prior to cycle 5, 9, 13... etc.). However, if the study treatment is delayed, scans can be delayed to correspond to the treatment schedule, and this will not be a deviation. CT scans will be done at the end of treatment visit only if patient has come off for reasons other than progression. Use of contrast according to institutional practice is recommended but not required.
14. Bone Scans if clinically indicated for evaluation of bone metastatic disease
15. For participants who opt in to the optional tissue collection, tissue may be collected at pre-screening from an urothelial carcinoma diagnostic procedure (soft tissue biopsy or TURBT) or during screening from a soft tissue biopsy (only for patients who do not sign the pre-screening ICF). Subjects are also offered the option of a fresh soft-tissue biopsy or TURBT again prior to treatment at cycle 4 or after. See Section 14 for details.
16. For participants who opt in to the optional blood collection, blood may be collected on C1D1, C2D1, C4D1, C7D1, C13D1, and at end of treatment. See Section 14 for details.
17. For participants who opt in to the optional stool collection, stool may be collected and stool questionnaire administered within 3 days prior to treatment on C1D1, C2D1, C4D1, C7D1, C13D1, and at end of treatment. See Section 14 for details.
18. Cabozantinib at dose specified in dose escalation and specified in section 6.2. Subjects will complete dosing diary for each cycle (Appendix I)
19. Pembrolizumab 200 mg IV q3weeks
20. End of treatment visit should occur within 28 (± 14) days after subject completes study treatment
21. Follow up visits: Patients will be followed via telephone contact or medical record review for survival 6 months after completing study treatment. Patients removed from therapy without evidence of progression will undergo radiological examination every 12 (± 1) weeks or earlier, if clinically warranted.
22. B type Natriuretic Peptide should be collected
23. Pre-screening ICF and eligibility review must be completed with 4 weeks prior to urothelial carcinoma diagnostic procedure (soft tissue biopsy or TURBT).

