9.3 On-Treatment Evaluations

Physical Exam – **at each cycle**

ECOG Performance Status – at each cycle

Vital Signs (Incl. weight) – at each cycle

Labs: (do not need to be repeated if screening labs performed within 14 days of C1D1)

- CBC w/diff – **at each cycle**
- CMP – Albumin, Alkaline Phosphatase, Aspartate Aminotransferase, Alanine Aminotransferase, Total Bilirubin, Calcium, Carbon Dioxide, Creatinine, Chloride, Glucose, Potassium, Protein, Sodium, Urea Nitrogen, phosphorous and magnesium. – **at each cycle**
- Additional Labs: LDH, Lipase, Lipid Panel, Gamma Glutamyl Transferase, N-type Natriuretic peptide – **at every fourth cycle (4, 8, 12...)**
- Coagulation – PT/INR, APTT – at every fourth cycle (4, 8, 12...)
- Thyroid function – TSH, Free T4, Free T3 – at every fourth cycle (4, 8, 12...)
- Serum pregnancy test (for women of childbearing potential) at every even cycle **(2, 4, 6...)**
- Urinalysis including urine protein creatinine ratio – **at every cycle**

ECG – at every fourth cycle (4, 8, 12...)

Safety assessment - Monitoring and recording all adverse events and serious adverse events using the CTCAE version 5.0 – **at each cycle**

Review of concomitant medications – **at each cycle**

CT scans of the chest/abdomen/pelvis and response assessment by RECIST v1.1 to be **repeated every 4th cycle**. However, if the study treatment is delayed, scans can be delayed to correspond to the treatment schedule, and this will not be a deviation.

Bone Scans if clinically indicated

Optional Tissue Collection for correlates at **cycle 4**, or after, see section 14

Optional Blood and Stool Collection and administration of Stool Questionnaire for correlates – **at C1D1, C2D1, C4D1, C7D1, C13D1** see section 14

Treatment with 200mg pembrolizumab per section 6.3

Treatment with appropriate dose of cabozantinib – review of patient dosing diary per section 6.2

9.4 End of Treatment Assessments (completed 28 days ± 14 days after completion of treatment)

Physical exam

Vital Signs

Concomitant medication collection

ECOG Performance status

Labs:

- CBC w/diff
- CMP – Albumin, Alkaline Phosphatase, Aspartate Aminotransferase, Alanine Aminotransferase, Total Bilirubin, Calcium, Carbon Dioxide, Creatinine, Chloride, Glucose, Potassium, Protein, Sodium, Urea Nitrogen. Phosphorus and magnesium
- Additional Labs: LDH, Lipase, Lipid Panel, Gamma Glutamyl Transferase, B-type Natriuretic peptide
- Thyroid function – TSH, Free T4, Free T3

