12 REGISTRATION GUIDELINES

Patients must meet all of the eligibility requirements listed in Section 5 prior to registration.

Study related screening procedures can only begin once the patient has signed a consent form. Patients must not begin protocol treatment prior to registration.

Treatment should start within five working days after registration.

To register eligible patients on study, complete a Clinical Trials Office Patient Registration Form and submit to: [contact].

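### The 72-hour pregnancy test is counted back from enrollment, so a compliant test can be about 10 days old at first dose

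*Combined protocol and SAP*

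**What the plan says.** **Pregnancy test.** Footnote 11 of the Study Calendar says the test "must be done at screening for all women of childbearing potential and every even cycle (2,4,6 ...etc.) during treatment" and "must be completed within 72hr prior to study enrollment". Section 9.3 gives the same on-treatment timing: "Serum pregnancy test (for women of childbearing potential) at every even cycle". Inclusion criterion 5.2.10 asks for a negative result at screening and sets no interval to first dose.

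**Start of treatment.** Section 12 says "Treatment should start within five working days after registration".

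**General laboratory rule.** Footnote 1 gives a four-week screening window but excepts "laboratory tests which need to be completed within 14 days prior to study treatment". Footnote 2 and Section 9.3 waive the C1D1 laboratory tests when a result no more than 14 days old exists. Section 9.3 lists the pregnancy test among the laboratory tests to which that waiver applies.

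**Haematology and chemistry.** Footnote 5 says the blood count "must be completed within 2 weeks prior to study enrollment". Footnote 6 says the chemistry panel "must be completed within 14 days prior to study enrollment at screening".

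**The concern.** A short limit on a pregnancy test is useful mainly if it runs up to first exposure. Here it runs up to enrollment, and a separate section allows a further interval before treatment. The 72-hour condition can be fully met and still say little about pregnancy status on the day of the first dose.

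The protocol itself shows why that day matters. Section 3.1.3 reports fewer live embryos and more implantation losses in rats given cabozantinib, and Section 7.3 warns of possible fetal harm from pembrolizumab. Pregnancy is an exclusion (5.3.28) and a reason for mandatory withdrawal from treatment (6.9). What is at stake is the safety of a small number of women, not any efficacy estimate.

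**Working it through.** The plan gives no figure for the age of the test at first dose, so there is nothing to reproduce. The check is calendar arithmetic.

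**Inputs**
- Pregnancy-test window: 72 hours = 3 days before enrollment (Section 8, footnote 11).
- Registration to treatment: five working days (Section 12).
- General laboratory limit: 14 days before treatment (Section 8, footnotes 1 and 2; Section 9.3).
- Assumption: enrollment in the footnotes and registration in Section 12 are the same date.

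**Step 1. Five working days in calendar days.** Counting forward from each day of the week:
- Monday to Friday registration: 7 days.
- Saturday: 6 days. Sunday: 5 days.
- With one public holiday inside the interval: 8 days for a weekday registration.

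**Step 2. Maximum age of a compliant test at first dose.** Age = window before enrollment + calendar length of five working days.
- Weekday registration: 3 + 7 = 10 days.
- Weekend registration: 3 + 6 = 9 or 3 + 5 = 8 days.
- Weekday registration with one holiday: 3 + 8 = 11 days.

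The ±3-day window for Day 1 of a cycle is left out, because it is unclear whether it extends the Section 12 interval. If it did, the weekday figure would be 10 + 3 = 13 days.

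**Step 3. Does another rule catch it?** The general rule rejects a result only when it is more than 14 days old. Ages of 8 to 13 days all pass. Footnote 11 and Section 9.3 name no test between screening and cycle 2.

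**Step 4. Effect of moving the anchor.** Counted to C1D1, the same 72-hour window gives a maximum age of 3 days instead of about 10.

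**Step 5. Haematology and chemistry.** Footnotes 5 and 6 count 14 days to enrollment; footnote 1 counts 14 days to treatment. Both can be met together, and the limit tied to treatment is the stricter one. A blood count taken 13 days before enrollment and 20 days before first dose meets footnote 5, fails footnote 1 and does not qualify for the footnote 2 waiver, so it has to be repeated. The permitted maximum is 14 days before treatment.

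**The case against.** **Ten days is a worst case.** It needs the earliest permitted test, the last permitted start day, and enrollment equal to registration. This stands and limits the size of the point. It does not remove it, because such a sequence complies with the plan. Section 12 is also worded as *should*, so a later start is not clearly barred until the 14-day limit applies.

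**The purpose of the 72 hours is not stated.** The documents treat the test as a screening eligibility check, and that its aim is to rule out pregnancy at first exposure is inference. This is fair. The point rests on what the text permits, read against the hazards the protocol describes.

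**Other safeguards exist.** Section 7.3 requires contraception and bars women unlikely to comply; 5.3.28 excludes women who are pregnant or expect to conceive, from the pre-screening or screening visit onward. These are real protections. However, Section 7.3 starts its requirement on the day medication begins (14 days earlier only for oral contraception), and none of these provisions supplies a test close to first dose.

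**The calendar grid may show a C1D1 test.** In the extracted text a mark appears in the cycle 1 column, but the column alignment is unreliable and footnote 11 names even cycles only. If a C1D1 test was meant and footnote 2 covers it, a 10-day-old result would still allow it to be waived.

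**Stronger readings that do not hold.** A reader might infer from footnotes 5 and 6 that blood counts and chemistry could be 14 + 7 = 21 days old at first dose. Footnote 1 forbids that. A reader might also object to the gap between the screening test and cycle 2. With tests at even cycles and three-week cycles, the planned on-treatment interval is 2 × 21 = 42 days, and the gap across the start of treatment is shorter than that, so it shows no defect.

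**Conclusion.** The point holds for the pregnancy test. The 72-hour limit is tied to enrollment, and a compliant test can be about 10 days old at first dose, roughly three times the stated window (10 / 3 ≈ 3.3). This assumes that enrollment and registration coincide and that treatment starts within the Section 12 interval. If enrollment came before registration, the test could be older, up to the 14-day laboratory limit.

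For haematology and chemistry the finding is only that two anchors appear in one table. The documents do not support a claim that stale results are permitted for those panels.

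The reach is small. The documents give no count of women of childbearing potential; few are expected among at most 39 patients. ORR, PFS6 and OS are unaffected. It is an inexpensive improvement to the wording.

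**What to change.** Reconcile footnote 11 with Section 12 and with footnotes 1 and 2, so that the existing 72-hour window is counted to the start of study treatment (C1D1), the anchor footnotes 1 and 2 already use. No new window is needed. State whether enrollment and registration are the same date.

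As a wording change only, give footnotes 5 and 6 the same anchor as footnote 1. No further eligibility check after registration is called for; Section 12 requires eligibility to be settled before registration, and that can stay as it is.

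The cost is an edit to three footnotes, one clarifying sentence, and an occasional repeat pregnancy test when treatment starts several days after registration.
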